## 4.3 Study visits and assessments

### 4.3.1 Schedule of assessments

**Table 2 Schedule of assessments for mothers Groups 1, 2, 3, 4 & 5**

|   | Screening Period | Treatment and follow-up Period |                |                            |                |                            |                |                            |  |                            |                            |                             |
|---|-------------------------|---------------------------------------|----------------|----------------------------|----------------|----------------------------|----------------|----------------------------|--|----------------------------|----------------------------|-----------------------------|
|   |                         | Screening                      | Visit 1 | Visit 2i | Visit 3 | Visit 4i | Visit 5 | Visit 6i | Visit 7                         | Visit 8m | Visit 9i | Visit 10i |
| Assessment                           | Day -14 to Day -1       | Day 0 21+0 to 23+6 weeks GA           | Day 3-5        | Day 26-30                  | Day 31-33      | Day 54-58                  | Day 59-61      | Day 82-86                  | Delivery up to 72 hours after delivery | 24-32 days post-delivery   | 84-96 days post-delivery   | 166-194 days post-delivery  |
| Informed consent                            | X                       |                                       |                |                            |                |                            |                |                            |  |                            |                            |                             |
| Inclusion/exclusion criteria                | X                       |                                       |                |                            |                |                            |                |                            |  |                            |                            |                             |
| Demography                                  | X                       |                                       |                |                            |                |                            |                |                            |  |                            |                            |                             |
| Medical and obstetric history               | X                       |                                       |                |                            |                |                            |                |                            |  |                            |                            |                             |
| Physical examination e           | X                       | X                                     |                | X                          |                | X                          |                |                            |  | X                          |                            | X                           |
| Obstetric examination                       | X                       | X                                     | X              | X                          | X              | X                          | X              | X                          |  |                            |                            |                             |
| Height l , weight, BMI           | X                       |                                       |                |                            |                |                            |                | X                          |  | X                          |                            | X                           |
| Vital signs a                    | X                       | X b                        | X              | X b             | X              | X b             | X              | X                          | X                                      | X                          | X                          | X                           |
| Urinalysis                                  | X                       | X                                     |                | X                          |                | X                          |                |                            | X                                      | X                          |                            |                             |
| Ultrasound result c              | X                       |                                       |                |                            |                |                            |                |                            |  |                            |                            |                             |
| Safety laboratory tests d        | X                       |                                       | X              | X                          | X              | X                          | X              | X                          |  |                            |                            |                             |
| Hep B, Hep C, HIV and syphilis k | X                       |                                       |                |                            |                |                            |                |                            |  |                            |                            |                             |
| Eligibility check                           |                         | X                                     |                |                            |                |                            |                |                            |  |                            |                            |                             |
| Randomisation                               |                         | X                                     |                |                            |                |                            |                |                            |  |                            |                            |                             |
| Contraindications vaccination check         |                         |                                       |                | X j             |                | X j             |                |                            |  |                            |                            |                             |
| Immunogenicity blood sample                 |                         | X
Predose                          |                | X
Predose               |                | X
Predose               |                | X                          | X                                      |                            |                            |                             |
| Vaccine/placebo administration              |                         | X                                     |                | X                          |                | X                          |                |                            |  |                            |                            |                             |
| Assessment of                               |                         | X                                     | X              | X                          | X              | X                          | X              | X                          |  |                            |                            |                             |

|   | Screening Period  | Treatment and follow-up Period |                      |           |                      |           |                      |           |  |                          |                          |                            |
|---|-------------------|--------------------------------|----------------------|-----------|----------------------|-----------|----------------------|-----------|--|--------------------------|--------------------------|----------------------------|
|   | Screening         | Visit 1                        | Visit 2 i | Visit 3   | Visit 4 i | Visit 5   | Visit 6 i | Visit 7   | Visit 8 m                   | Visit 9 i     | Visit 10 i    | Visit 11 i      |
| Assessment                             | Day -14 to Day -1 | Day 0 21+0 to 23+6 weeks GA    | Day 3-5              | Day 26-30 | Day 31-33            | Day 54-58 | Day 59-61            | Day 82-86 | Delivery up to 72 hours after delivery | 24-32 days post-delivery | 84-96 days post-delivery | 166-194 days post-delivery |
| injection site and immediate AEs f |                   |                                |                      |           |                      |           |                      |           |  |                          |                          |                            |
| Instruct 7-day-eDiary                         | X                 |                                | X                    |           | X                    |           |                      |           |  |                          |                          |                            |
| Review eDiary and transfer data incl. AE/CM   |                   | X                              | X                    | X         | X                    | X         | X                    |           |  |                          |                          |                            |
| Urine pregnancy test                   |                   |                                |                      |           |                      |           |                      | X         |  | X                        |                          | X g             |
| AE check                               |                   |                                |                      |           |                      |           |                      |           |  |                          | X h           |                            |
| CM check                               |                   |                                |                      |           |                      |           |                      | X         |  |                          | X h           |                            |

**Footnotes**

- a. Heart rate, blood pressure and oral temperature.
- b. Vital signs at vaccination visits will be recorded pre-dose and at 30 min post-dose prior to discharge.
- c. Last available ultrasound results, as per UK, DK or SA schedules, for confirmation of no detectable congenital abnormalities and singleton pregnancy.
- d. Haematology (red blood cell count, haemoglobin, haematocrit, platelet count, MCV, MCHC, white blood cell count with absolute differential (neutrophils, lymphocytes, monocytes, eosinophils, basophils counts) and biochemistry (sodium, potassium, blood urea, creatinine, creatine kinase, glucose, calcium, albumin, cholesterol, C-reactive protein, triglycerides, phosphorus (inorganic phosphate), lactate dehydrogenase, total protein, globulin, uric acid, alkaline phosphatase, aspartate aminotransferase, alanine aminotransferase, gamma-glutamyl-transferase, total bilirubin and direct bilirubin). If delivery before a scheduled safety laboratory test visit, it is performed at delivery.
- e. Full physical examinations Screening & Visit 11. Targeted physical examinations remaining visits.
- f. Photographs may be taken of injection site reactions as required. At vaccination visits (only), check immediate adverse reactions.
- g. Any participant found to be pregnant at the end of the study will be followed up, as regards if their baby is healthy at delivery.
- h. From Delivery (Visit 8) and onwards, only MAAEs, AEs of special interest (AESI), e.g., GBS disease, autoimmune disease and immune-mediated reactions, or SAEs, and CMs prescribed for such events are reported.
- i. Visit 2, Visit 4, Visit 6 and Visit 9-11 may be home visits.
- j. There is contraindications check at V3 (incl. assessment of safety laboratory tests from V2) and at V5 (incl. assessment of safety laboratory tests from V4) before the vaccinations.

Sponsor: **MINERVAX**  
IMP: GBS-NN/NN2  
Study ID: MVX0004

CONFIDENTIAL  
Clinical study protocol

14-Apr-2023  
Version 5.0  
Page 29 of 75

- k. Last available Hep B, Hep C, HIV and Syphilis results, as per UK, DK or SA schedules. Only if no results are available, new samples are taken.
- l. Height measurement only at screening.
- m. If a participant delivers after V1, but before completing all pre-delivery visits, additional safety laboratory tests are taken at Delivery (V8).

**Table 3 Schedule of assessments for babies**

| Assessment                      | Visit 8           | Visit 9h | Visit 10h | Visit 11h |
|--|--------------------------|----------------------------|-----------------------------|-----------------------------|
| Delivery up to 72 hours after delivery | 24-32 days post-delivery | 84-96 days post-delivery   | 166-194 days post-delivery  |                             |
| Demography                             | X                        |                            |                             |                             |
| Gestational history a       | X                        |                            |                             |                             |
| Physical examination                   | X                        | X                          | X                           | X                           |
| Head circumference                     | X                        | X                          | X                           | X                           |
| Length                                 | X                        | X                          | X                           | X                           |
| Weight                                 | X                        | X                          | X                           | X                           |
| Apgar score b               | X b           |                            |                             |                             |
| Vital signs c               | X                        | X                          | X                           | X                           |
| Developmental milestones f  |                          | X                          | X                           | X                           |
| Immunogenicity blood sample            | X d           | X e             | X e              |                             |
| AE check                               |                          | X                          |                             | X g              |
| CM check                               | X                        |                            |                             | X g              |

**Footnotes**

- a. Gestational age and gender.
- b. Apgar score at 1, 5 and 10 minutes if available (available scores will be collected, 'not recorded' will be an option).
- c. Heart rate (actual, not Apgar score).
- d. Cord blood or infant blood (heel prick or venous sample) within 72 hours of birth.
- e. Heel prick or venous sample.
- f. Age-appropriate developmental milestone check.
- g. After the first 28 days of age, only MAAEs, AEs of special interest (AESI), e.g., GBS disease and abnormal development according to developmental milestones, or SAEs, and CMs prescribed for such events until 180 days of age.
- h. Visit 9-11 may be performed as home visits.

#### 4.3.2 Description of individual study visits

##### VISITS FOR MOTHERS:

###### Screening, Day -14 to Day -1: Eligibility assessment:

Obtain informed consent, check eligibility against the in/exclusion criteria, obtain and record demography, medical and obstetric history, current medication (including supplements and over the counter preparations), conduct a full physical examination (respiratory, cardiovascular, gastrointestinal, gross central nervous system, gross musculoskeletal) by a physician, obstetric examination\* (fundal height, foetal movement and foetal heart rate), measure and record height and weight (for calculation of BMI), vital signs (heart rate, blood pressure, oral temperature). Collect samples for urinalysis, safety laboratory tests (haematology and serum biochemistry), determination of subject's Hep B, Hep C, HIV and syphilis status (assessment based on results from last samples taken in first trimester, if available, otherwise samples are taken at the screening visit), record result of the last ultrasound for the assessment of the subject's eligibility for inclusion in the study. Subjects will be contacted by phone and informed if they are eligible to proceed from screening, and, if eligible, to confirm the appointment for Visit 1, Day 0, where they will be randomised and assigned to one of the Groups 1 to 5, see Table 1.

###### Visit 1, Day 0: Randomisation, 21+0 to 23+6 weeks GA:

Eligibility check - participants who remain eligible will be randomised according to the randomisation schedule. The randomisation will allocate participants to a specific group. Visit 1, Day 0, is at the planned time of the 1st vaccination which is 21+0 to 23+6 weeks GA, as established by first/second trimester ultrasound examination.

Only unblinded study team members, responsible for dispensing and injecting vaccines/placebo, or for checking related procedures and records, will have access to any information regarding the actual products injected to the subjects, and this information will not be revealed to blinded study team members.

The actual injection of vaccine/placebo will be performed by unblinded study team members, or alternatively by blinded study team members by use of syringes with opaque tape, to avoid unblinding during the injections.

The following will be undertaken, and results recorded:

Targeted physical examination\* (respiratory, cardiovascular), obstetric examination\* (fundal height, foetal movement and foetal heart rate), vital signs (pre- and 30 minutes post-vaccination), urinalysis, pre-vaccination immunogenicity maternal blood sample, and injection of vaccine/placebo. Before the subject leaves the site: Assessment of the injection site, check immediate adverse reactions, and give access to and instruct in the 7-day-eDiary.

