|---------------------|--|

|                                     |   |
|-------------------------------------|---|
| Investigational medicinal products  | 
Group B Streptococcus Vaccine (GBS-NN/NN2) mixed with Alhydrogel.
 
The final unit dose of GBS-NN/NN2 will contain a sterile suspension of injection of 50 µg of the two fusion proteins in an isotonic buffer and 0.5 mg of aluminium in a volume of 0.5 mL.
 
The Placebo will be 0.9 % saline sterile solution for injection, purchased locally by the investigational sites.
 
The Vaccine and Placebo are visibly distinguishable; therefore, to ensure the blinding of the study is maintained, it will be ensured that a separate unblinded study team will administer the injections, or that syringes with opaque tape will be used, preventing the contents being identified.
   |
| Dosages and route of administration | 
Each injected dose of 0.5 mL GBS-NN/NN2 contains 50 µg of GBS-NN, 50 µg of GBS-NN2 and 0.5 mg of aluminium for all groups and vaccination regimens.
 
Each injected dose of 0.5 mL Placebo consists of 0.9 % saline for all groups and vaccination regimens.
 
Administration will be by intramuscular injection, preferably into the non-dominant arm. The dominant arm may be used if it is not possible to administer into the non-dominant arm e.g., due to an ongoing injection site reaction, or a tattoo making assessment of the injection site difficult.
   |

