#### 4.3.3.1 Diaries

The subject will get access to an electronic diary (eDiary) at the study visit where vaccine/placebo is administered. In the eDiary, details of solicited local and systemic reactions will be recorded, for 7 days after each of the vaccinations (the day of the vaccination and the following 6 days).

For solicited local injection site reactions (*redness, swelling, pain, tenderness, itching*) and *pyrexia* (oral temperature  $>37.9^{\circ}\text{C}$ ), the diameters and temperatures will be measured, by use of rulers and thermometers, and recorded in the eDiary.

For solicited systemic reactions (*nausea, vomiting, diarrhoea, headache, fatigue, myalgia*), intensities (*mild, moderate, or severe*) will be recorded in the eDiary. In addition, other AEs, i.e., unsolicited AEs, including MAAEs, SAEs, concomitant medication (CM) or vaccines will also be recorded and assessed in the eDiary.

The solicited local and systemic reactions, recorded in the eDiary, will be assessed by the site staff.

If serious, the SAEs will undergo evaluation as per the current reference safety information of the IB, as described in section 6.

Details on *new medical problems* (unsolicited AEs), *visits to a doctor* (MAAEs) or *visits to a hospital* (SAEs) or *new medication* (CM) recorded in the diary will be assessed by the investigator at the visits 28 days following each vaccination, as described in section 6.

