## 5 Investigational products

The investigational products will only be administered to participants included in this study and only according to the procedures described in this protocol.

Only the unblinded study team members (incl. site staff and monitor), may handle/check and have access to the investigational products and will be responsible for procedures for receipt, storage, and monitoring of storage conditions of the investigational vaccine/placebo, and for the assembly, dispensing and injection of vaccine/placebo in the study. Alternatively, the actual injection of vaccine/placebo may be performed by blinded study team members by use of syringes with opaque tape, to avoid unblinding during the injections.

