### 5.1 Identity and description of the investigational vaccine

The vaccine antigen, “(NN+NN2) DP”, is a *clear, colourless to slightly yellow* sterile solution for injection, filled into vials. The vaccine adjuvant, Alhydrogel®, is a *white to slightly yellow uniform cloudy white suspension which may sediment during storage* sterile suspension for injection, filled into vials.

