### **5.3 Dosing and administration of investigational and placebo vaccines**

The study vaccines may only be administered by authorised staff as indicated in the investigational site signature and delegation form.

For all groups in the study, and for investigational product, as well as placebo (saline), a dose of 0.5 mL sterile suspension (investigational vaccine) or solution (saline) for injection, is injected intramuscularly into the deltoid muscle, preferably of the non-dominant arm, at each dosing occasion.

Each vial and box of investigational vaccine and placebo (saline) are labelled, indicating the type of product, and thus the identity of the product (investigational vaccine / placebo) will be known to the unblinded site staff responsible for dispensing and injection procedures and maintenance of the related records, as well as to the unblinded monitor, checking these procedures and records.

The unblinded site staff and the unblinded monitor will not reveal the identity of the injected vaccine/placebo to any blinded study team member, including the blinded site staff, responsible for the safety assessments, and the blinded monitor. For more details on blinding and breaking the blind, please see Section 5.6.

The blinded study team members will verify eligibility for vaccination (per Sections 4.6.2 and 4.6.3 or 4.7.2, as applicable, depending on 1st, 2nd or 3rd dose) including measuring pre-vaccination vital signs, and will refer the subject to vaccination, to be performed by the unblinded study team members, or alternatively by blinded study team members, by use of syringes with opaque tape, to avoid unblinding during the injections.

Administration of investigational vaccine / placebo:

- Check that the shelf-life of 24 hours for the assembled investigational vaccine has not expired and check the participant number on the label of the vial, see Section 5.7.2.
- Invert the vial gently prior to drawing up the suspension / solution with a sterile disposable syringe fitted with a needle
- Draw up 0.5 mL of investigational vaccine / placebo (saline) for administration
- Injections must be given deeply intramuscularly, preferably in the subject's non-dominant arm in the deltoid muscle. The dominant arm may be used if it is not possible to administer into the non-dominant arm (e.g., due to an ongoing injection site reaction, or a tattoo making assessment of the injection site difficult)

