## 7.12 Interim analysis

An early analysis of data available up to, and including, Visit 8 will be performed based on unblinded cleaned data. The analysis will include the primary immunological endpoint for IgG antibodies specific to the AlpN proteins in cord blood, the key secondary safety endpoints in all study participants (maternal participants and babies), and the secondary immunological endpoint for IgG antibodies specific to the AlpN proteins in maternal blood.

The early analysis will be conducted by an unblinded team within the CRO and the sponsor. Separate teams within the CRO and the sponsor will remain blinded until the end of the study to ensure further study execution in a blinded manner. Investigators, and site personal and study participants will remain blinded until the end of the study.

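### When unblinded staff inject, the protocol states no measure that hides the visibly different syringe contents from the woman, who records and rates her own solicited reactions

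*Protocol*

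**What the plan says.** The synopsis says of the two products: "The Vaccine and Placebo are visibly distinguishable". It then gives the safeguard as a choice: "a separate unblinded study team will administer the injections, or that syringes with opaque tape will be used, preventing the contents being identified".

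Three places in the body of the protocol say who injects and when tape is used:

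- Section 4.3.2, Visit 1: "performed by unblinded study team members, or alternatively by blinded study team members by use of syringes with opaque tape".
- Section 5: "the actual injection of vaccine/placebo may be performed by blinded study team members by use of syringes with opaque tape", offered as the alternative to injection by the unblinded team.
- Section 5.3, for first, second and third doses: "to be performed by the unblinded study team members, or alternatively by blinded study team members, by use of syringes with opaque tape".

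Section 5.1 describes the adjuvant as a "uniform cloudy white suspension which may sediment during storage". Under section 5.2 it supplies 0.5 mL of the 0.7 mL mixture.

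On the participant's status, protocol 7.12 says that "study participants will remain blinded until the end of the study", and SAP section 6 says the same.

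On who generates the reactogenicity data, section 4.3.3.1 says: "In the eDiary, details of solicited local and systemic reactions will be recorded, for 7 days after each of the vaccinations". Section 6.4 confirms that the subject does the rating, and section 3.6 lists solicited local and systemic reactions as key secondary safety endpoints in the mother.

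**The concern.** Two groups need to be kept from seeing the syringe: the blinded staff who assess safety, and the woman herself. The written safeguard deals with the first. A separate unblinded injector, or a taped syringe in a blinded injector's hands, keeps the assessors blind. Only the taped syringe also keeps the woman blind, and outside the synopsis tape is named only for blinded injectors.

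This matters because the reactogenicity data begin with her. Pain, tenderness, itching, nausea, vomiting, diarrhoea, headache, fatigue and myalgia are reported by the woman, and several of them are common in pregnancy anyway. If she knows or guesses what she received, a vaccine-versus-saline difference in these items mixes the vaccine's effect with her expectation. Section 6.4 treats solicited reactions as related by definition, so no causality judgement filters such a report later. Section 2.5 says that the safety results, together with cord-blood IgG, inform which regimen goes to phase III.

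**Working it through.** The plan gives no figure to reproduce here. The check compares the relevant passages and then counts the injections.

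**Step 1. Can the products be told apart?** Yes, by the synopsis's own statement. That saline is clear and the assembled vaccine cloudy is an inference from sections 5.1 and 5.2 and the synopsis. The argument does not need it.

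**Step 2. What is stated for each injection route?**

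| Route | Masks blinded staff | Masks the woman |
|---|---|---|
| Unblinded staff inject | Yes: separate team, duty not to disclose | No measure stated |
| Blinded staff inject | Yes: opaque tape | Yes: the same tape |

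The synopsis offers tape without saying who injects. The link to blinded injectors comes from 4.3.2, 5 and 5.3. Section 4.2 presents the unblinded administering team as the design and does not mention tape.

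**Step 3. Do the non-disclosure rules fill the gap?** Section 4.3.2 limits product information to unblinded team members, and it and section 5.3 forbid passing that information to blinded team members. Neither names the participant or says how her view is blocked. Section 5.3 lists checking the vial label, inverting the vial and drawing up the dose among the administration steps, and says that vials are labelled by product type. It does not require this to be done out of her sight.

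**Step 4. Is the participant meant to be blinded?** Protocol 7.12 and SAP 6 both say so.

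**Step 5. How many injections could be affected?** From protocol Table 1:

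| Gestational age | Vaccine | Saline |
|---|---|---|
| 22 weeks | Groups 2, 3: 60 + 60 = 120 | Groups 1, 4, 5: 60 + 60 + 30 = 150 |
| 26 weeks | Groups 1, 2, 4: 3 × 60 = 180 | Groups 3, 5: 60 + 30 = 90 |
| 30 weeks | Groups 1, 3: 60 + 60 = 120 | Groups 2, 4, 5: 60 + 60 + 30 = 150 |
| Total | 420 | 390 |

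420 + 390 = 810 = 270 × 3. The 22-week split of 120/270 agrees with the 12/27 given in protocol 6.7.

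Groups 1 to 4 (4 × 60 = 240 of 270 women) are planned to receive both products, so a woman who could see the syringe could also compare her own visits. SAP 4.7.1 tabulates solicited events by vaccination number, which sets vaccine against saline at each visit.

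**Step 6. What share is exposed?** The documents do not give the split between routes, so the range is 0 to 100% of at most 810. This is a ceiling, because vaccination may be stopped (section 4.7) and some women may deliver before all visits are complete (section 4.3.2, Visit 8).

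**The case against.** The strongest reply is that the detail may be in documents that were not available. Protocol 5.6 refers to a study-specific blinding manual if applicable, SAP 2.4 says without qualification that such a manual gives more detail, and protocol 5.2 and 5.3 refer to a pharmacy manual. A screen, tape or an instruction to look away could be in any of these. This stands. The point concerns the written protocol, and whether the manuals close the gap is unknown.

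Second, the trial is labelled observer-blind, which section 4.2 explains as separating the administering team from the assessing team. The statements that participants are blinded sit in the interim-analysis sections, where the subject is who stays blinded during the early analysis. It is fair that those sentences do not describe masking at injection. They do show that both documents regard participants as blinded, so the label alone does not settle the matter.

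Third, the woman is not the only assessor. Site staff assess the diary entries (4.3.3.1), blinded staff inspect the injection site before she leaves (5.3), the investigator judges severity for the halting rule (6.8), and ratings follow a published toxicity scale (6.1). This narrows the exposure. It does not remove expectation from a report of pain, headache or fatigue, and redness, swelling and temperature are measured by the woman herself.

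Fourth, safety is summarised descriptively, with no test of vaccine against saline, and the primary endpoint is a laboratory assay. Both are correct and limit the consequence.

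A reader might infer that women were in fact unblinded, or that the whole protocol confines tape to blinded injectors. The documents support neither reading. They show a missing safeguard, not an event, and the synopsis does not attach tape to any type of injector. Effects on unsolicited reporting or on return for later doses are possible, but nothing in the documents demonstrates them.

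**Conclusion.** The point holds as a gap in the written safeguard. For injection by unblinded staff, the protocol and SAP state no measure that hides visibly different products from a participant whom both documents call blinded. The consequence is possible expectation bias in the self-reported part of the descriptive key secondary reactogenicity data. The documents give no ground for extending it to the primary cord-blood IgG endpoint.

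The size is unknown: between none and all of at most 810 planned injections. The conclusion rests on two assumptions. At least some sites use unblinded injectors, and the manuals that were not available add no masking of the participant. If the manuals already require it, what remains is to bring that rule into the protocol. The change is worth making, but it does not threaten the trial's main conclusions.

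**What to change.** In the synopsis and in protocol sections 4.3.2, 5 and 5.3, replace the either/or with one rule: every syringe, vaccine or saline, is prepared out of the participant's sight and covered with opaque tape, whoever injects. Keep the separate unblinded preparation team. Align the blinding and pharmacy manuals.

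Other means, such as a screen, could also close the gap. Tape is the natural choice because the protocol already accepts it on one route.

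The cost is tape and a wording change, with no added visits or data. The small drawback is that syringe graduations are harder to see, which sites on the taped route already accept.

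The documents do not say whether dosing is complete. If it is, report the injection route by site in the study report, and qualify the statement that participants were blinded wherever unblinded staff injected without tape or another recorded means of masking.
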